10.4.3 Secondary Analyses

No secondary analyses or subgroup analysis is planned.

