3. STUDY OBJECTIVES

Overall Objective

The purpose of this study is to evaluate whether daily intake of erythritol or xylitol over a period of 7 weeks will alter gut microbiota composition and glucose tolerance.

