3.2 Primary Objective

Glycaemic control (fasting insulin & glucose & c-peptide after oral glucose challenge)

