3.3 Secondary Objectives

- Human gut microbiota composition
- Metabolomics
- Blood lipids, hepatic enzymes
- Inflammatory response
- Intestinal permeability
- Gastrointestinal tolerance (bloating, diarrhoea etc.)
- Intestinal glucose absorption

Safety Objectives

The study also aims to assess tolerability in terms of incidence of gastrointestinal side effects of the two polyols.

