4.2 Secondary Outcomes

- Human gut microbiota composition: Faecal samples will be taken before and after treatment and the taxonomic and functional profiles of the gut microbiota will be assessed by metagenomic shotgun sequencing.
- Metabolomics: Faecal and urine samples will be used for analysis of the metabolome using metabolomics.
- Blood lipid profile, hsCRP and hepatic enzymes: Fasting samples will be taken to measure triglyceride, total cholesterol, LDL and HDL levels, and the liver enzymes ASAT (aspartate transaminase) and ALAT (alanine transaminase). The analysis will be carried out in the hospital laboratory (St. Claraspital).
- **Inflammatory response:** As erythritol might act as a radical scavenger and reduce oxidative stress, we plan to assess inflammatory state by measuring IL-6, TNF-α, sTNFR1, sTNFR2, high sensitive CRP (hsCRP) and leucocytes.
- Intestinal permeability: Circulating markers of intestinal permeability (zonulin, LPS) will be measured.
- Gastrointestinal tolerance (bloating, diarrhoea etc.): We will assess gastrointestinal symptoms by using a validated questionnaire (Clinical rating scale for gastrointestinal symptoms: Svedlund et al.²¹). The questionnaire will be used at baseline and at the end of week 3 and 7 (self-reporting). A license agreement will be sent to AstraZeneca (ASTRAZENECA AB, 556011-7482 S-151 85 Södertälje, Sweden).
- 4.3 Intestinal Glucoseabsorption: We will assess intestinal glucose absorption by use of a validated technique: during the oral glucose tolerance test, 3g of 3-O-Methyl-Glucose (3-OMG) is ingested. 3-OMG is then measured in the plasma samples obtained at 0-30-60-90-120min. Other Outcomes of Interest

We accept that a possible confounder might be the substitution of sucrose in daily life as polyols might serve as a substitute. If sugar consumption is reduced, metabolic effects could be caused by reduced sugar exposure rather than polyol intake. We will therefore assess overall sugar consumption before and during the trial. Participants will keep a food diary. For this purpose we will use the clinical diary used by our nutritionists for preoperative assessment of bariatric patients.

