10.4 Planned Analyses

10.4.1 Datasets to be analysed, analysis populations

In this pilot trial which is purely observational, an analysis per protocol is planned. Drop-outs will be replaced, but baseline data of drop-outs might be included to characterize the baseline population. Baseline values of all three groups will be compared, to rule out any baseline differences. The control group will also be examined twice, and the two time-points should yield similar results. Data from each participant before and after treatment will be analyzed in the sweetener groups. In that way, each participant will serve as his or her own control. Post-treatment values of both treatment groups will then be compared to the control group (without treatment).

In case both sweeteners should have an effect on our endpoints, we might combine the two arms for an additional analysis comparing "no sweetener" (n= 20) vs. "sweetener" (n= 40).

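### Section 10.4.3 says no secondary analyses are planned, which contradicts the gut microbiota objective and the seven listed secondary objectives

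*Protocol*

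**What the plan says.** The overall objective in section 3 has two parts: whether seven weeks of either sweetener "will alter gut microbiota composition and glucose tolerance". The study title names the same two parts.

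Section 3.2 takes only the second part as primary: "Glycaemic control (fasting insulin & glucose & c-peptide after oral glucose challenge". Section 3.3 lists seven secondary objectives, from "Human gut microbiota composition" to "Intestinal glucose absorption". Section 4.2 describes the measurements; for microbiota, "the taxonomic and functional profiles of the gut microbiota will be assessed by metagenomic shotgun sequencing". The glucose-absorption outcome (3-OMG) is printed under the number 4.3. That is only a layout matter, but replacement text that cites 4.2 alone would miss it.

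On analysis:
- Section 10.4.1 gives generic comparisons (before against after in the sweetener arms, post-treatment values against control) without naming endpoints. It adds that, if both sweeteners have an effect, "we might combine the two arms for an additional analysis".
- Section 10.4.2, headed as the primary analysis, names demographics and the hormone and glucose curves. It gives one-way ANOVA and paired t-tests, with significance at P < 0.05 and no adjustment.
- Section 10.4.3 states: "No secondary analyses or subgroup analysis is planned".
- Section 10.4.5 compares adverse events between groups.
- Section 11.5, on data protection, says the microbiota raw data will be correlated with other findings, glucose tolerance among them.

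**The concern.** The protocol collects stool, urine and blood for seven secondary objectives, one of which is also half of the overall objective, and then says that no secondary analysis is planned. A protocol may leave analytic detail to a SAP. Here, however, the protocol makes a positive statement, and a SAP that specified such analyses would contradict it.

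The microbiota outcome carries weight in the trial's reasoning. Section 10.1 offers favourable microbiota changes as a possible explanation of any glycaemic improvement. If its analysis is chosen after the data are in, that explanation is hard to defend. If the primary methods are carried over to sequencing and metabolome data unchanged, chance findings will accumulate at the nominal 5% rate.

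**Working it through.** The point is mainly textual, and the plan gives no figure for it that could be reproduced. The arithmetic below only sizes the second reading.

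**Step 1: the texts side by side**

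| Outcome group (3.3) | Measured in section 4? | Method for it in section 10? |
|---|---|---|
| Gut microbiota | yes | none named; a correlation is mentioned in 11.5 |
| Metabolomics | yes | none named |
| Lipids, liver enzymes | yes | none named |
| Inflammation | yes | none named |
| Permeability | yes | none named |
| Gastrointestinal tolerance (GSRS) | yes | partly: GSRS is also the safety outcome (4.4, 8.2.4.1), and 10.4.5 compares adverse events |
| Glucose absorption (3-OMG) | yes | none named |

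That leaves two readings of 10.4.3. Under the literal reading, six of the seven groups have no planned analysis. Under the generous reading, the generic comparisons of 10.4.1 cover them, and then 10.4.3 is untrue as written. Either way the sentence needs correcting.

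**Step 2: size under the generous reading**

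Inputs: α = 0.05 per test with no adjustment (10.4.2). For m tests with no true effect:
- expected false positives = α × m (independence not needed);
- chance of at least one = 1 − (1 − α)^m (assumes independence; positively correlated outcomes would give less).

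Single-number variables that can be counted from section 4.2, the five GSRS scales in 8.2.2 and 3-OMG: 4 lipids + 2 liver enzymes + 6 inflammation markers (IL-6, TNF-α, sTNFR1, sTNFR2, hsCRP, leucocytes) + 2 permeability markers + 5 GSRS scales + 1 summary of 3-OMG = 20. Three tests per variable means one ANOVA plus a paired t-test in each of the two sweetener arms.

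| Family | m | Expected false positives | Chance of at least one |
|---|---|---|---|
| One test per secondary objective | 7 | 0.05 × 7 = 0.35 | 1 − 0.95^7 = 30.2% |
| One test per variable | 20 | 0.05 × 20 = 1.0 | 1 − 0.95^20 = 64.2% |
| One test per variable, GSRS left out | 15 | 0.05 × 15 = 0.75 | 1 − 0.95^15 = 53.7% |
| Three tests per variable | 60 | 0.05 × 60 = 3.0 | 1 − 0.95^60 = 95.4% |

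Taxa, microbial functions and metabolites are in none of the variable counts.

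**Step 3: sequencing and metabolome features**

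For F features tested one by one, the expected number of false positives per comparison is 0.05 × F. The protocol does not give F. As an assumption only, F = 100 gives 0.05 × 100 = 5 and F = 300 gives 0.05 × 300 = 15 per comparison and data type.

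**The case against.** The best defence is that 10.4.3 pairs secondary with subgroup analysis, so it may mean only that nothing is planned beyond what has already been described. Section 10.4.1 precedes both the primary and the secondary heading, is not limited to glycaemia and speaks of endpoints in the plural. Section 11.5 intends a microbiota correlation. This stands as evidence of what the team means to do. It does not rescue the sentence, because nothing in the text gives it that narrower meaning.

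A reader might go further than the documents allow in five ways:
- **That half of the trial's question will not be analysed at all.** Sections 10.4.1 and 11.5 show that analyses are intended; what is contradictory is the plan.
- **That GSRS is collected for nothing.** It doubles as a safety outcome, and adverse events are compared between groups.
- **That the pooled-sweetener analysis contradicts 10.4.3.** It is conditional and optional, so it can coexist with a statement about what is planned.
- **That the microbiota result would be fully post hoc.** The outcome, sampling times and laboratory method are fixed in advance; the statistical method is not.
- **That a definite count of false positives, such as 15 to 45 per data type (100 to 300 features × 3 tests × 0.05), is built in.** The protocol gives no feature count and does not say that features are tested singly. Only the 5% rate per comparison follows from it, and only if they are.

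It is also fair to say that an exploratory pilot need not adjust for multiplicity, and that a particular community-level test or distance measure belongs in a SAP. Both points stand. The difficulty is that section 10.1 declares hypothesis testing not applicable while 10.4.2 sets a significance threshold, so an exploratory reading is not secured by the text.

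**Conclusion.** The contradiction is real and explicit. Section 10.4.3 cannot be reconciled with the overall objective, the seven secondary objectives and the outcomes in section 4, and it conflicts with the comparisons implied in 10.4.1 and 11.5. Read literally, six of the seven outcome groups lack a planned analysis, with GSRS partly covered.

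Read generously, they would be tested by before-after t-tests and ANOVA at an unadjusted 5%. For the 20 countable variables, that is between 1.0 (one test each) and 3.0 (three tests each) expected false positives if nothing has an effect. For sequencing and metabolome features it is about 5% of those tested in each comparison. These sizes assume no true effect and, for features, testing one by one. The number of features is unknown.

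The trial's design and its primary outcome are not affected. The sentence is wrong, and correcting it costs almost nothing.

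**What to change.** Replace the sentence in 10.4.3 with:

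> All secondary outcomes (section 4.2 and intestinal glucose absorption) are analysed as each sweetener versus control, adjusted for the baseline value, with 95% confidence intervals, and are labelled exploratory. Single taxa, functions and metabolites are reported with false-discovery-rate control, with details in the SAP. Apart from the optional pooled-sweetener comparison in 10.4.1, no further or subgroup analyses are planned.

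This does slightly more than remove the contradiction. A baseline-adjusted comparison uses the randomised control arm and the baseline measurement together. A before-after test in a sweetener arm leaves out the control arm, and a comparison of post-treatment values leaves out the baseline. The choice of community-level test, distance measure and false-discovery level can stay in the SAP.

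The cost is one paragraph and modest extra analysis, with no change to visits, samples or participants. The downside is that fewer single taxa, functions or metabolites will be called significant.

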10.4.4 Interim analyses

We do not plan any interim analysis.

10.4.5 Safety analysis

Any advert events are listed and treatment groups are compared.

10.4.6 Deviation(s) from the original statistical plan

Any deviations from the original statistical plan will be reported and justified in the final report.

10.5 Handling of missing data and drop-outs

Missing data: as a basic principle, we will only analyse available data. In case of single missing blood values, a "last observation carried forward" (LOCF) approach will be used. Drop-outs will be replaced. Data from drop-outs will be included in the analysis if feasible (e.g. baseline values can be of value to characterize the study population).

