4. STUDY OUTCOMES

4.1 Primary Outcome

Glycemic control: Before and after treatment, an oral glucose tolerance test will be carried out. In this trial, we will include more time-points (0-30-60-90-120min. after glucose ingestion) for an accurate assessment of pharmacokinetics (AUC: area under the curve, Cmax, Tmax).

STANDARD ORAL GLUCOSE TOLERANCE TEST: DEFINITIONS

Diabetes: Fasting plasma glucose ≥7.0mmol/l or ≥11.1mmol/l (OGGT: 2-h plasma glucose))

Impaired Glucose Tolerance (IGT): Fasting plasma glucose <7.0mmol/l and ≥7.8 and <11.1mmol/l (OGGT: 2-h plasma glucose)

Impaired Fasting Glucose (IFG): Fasting plasma glucose 6.1 to 6.9mmol/l and <7.8mmol/l (OGGT: 2-h plasma glucose).

Definition and Diagnosis of Diabetes Mellitus and Intermediate Hyperglycaemia: Report of a WHO/IDF consultation. World Health Organization 2006

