8.2 Assessments of outcomes

8.2.1 Assessment of primary outcome

Oral glucose tolerance test (OGTT):

At baseline and after the treatment period (ca. 49d plus 3 days) an oral glucose tolerance test is carried out.

Patients are instructed:

- that they should not have been acutely ill (acute infection of any kind) within 14 days prior to OGTT.
- to abstain from strenuous exercise within the last 48h before OGTT,
- to make sure their main meals within the last 48h before OGTT include carbohydrates,
- that they must not eat or drink, nor consume alcohol or smoke within 10 hours before OGTT.

Blood sampling: After an overnight fast of at least 10 hours an antecubital catheter will be inserted into a forearm vein for blood collection. After a fasting blood sample on ice into 7.5mL tubes containing EDTA (6 µmol/L) the participant will ingest a 75g glucose solution (300 ml OGTT syrup, Roche) within 5-10min.

Further blood samples will be taken at regular time intervals (30, 60, 90, and 120 min).

Tubes will be centrifuged at 4° C at 3000 rpm for 10 min and 4 plasma sample aliquots are pipetted into 1.5mL tubes (aliquots à 600μ L plasma each; tubes labelled: ① Insulin/Glucose, ② C-Peptide, ③ Reserve 1, ④ Reserve 2). Samples will be stored at -80° C until analysis of plasma glucose, insulin and C-peptide.

STANDARD ORAL GLUCOSE TOLERANCE TEST: DEFINITIONS

Diabetes Fasting plasma glucose ≥7.0mmol/l or ≥11.1mmol/l (OGGT: 2–h plasma glucose))

Impaired Glucose Tolerance (IGT) Fasting plasma glucose <7.0mmol/l and ≥7.8 and <11.1mmol/l (OGGT: 2-h plasma glucose)

Impaired Fasting Glucose (IFG) Fasting plasma glucose 6.1 to 6.9mmol/l and <7.8mmol/l (OGGT: 2-h plasma glucose)

- > OGTT: venous plasma glucose 2-h after ingestion of 75g oral glucose load

Definition and Diagnosis of Diabetes Mellitus and Intermediate Hyperglycaemia: Report of a WHO/IDF consultation. World Health Organization 2006

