10.4.2 Primary Analysis

Descriptive statistics will be used for demographic variables, such as age, weight, height and BMI. Hormone and glucose profiles will be analyzed by calculating the area under the concentration-time curve (AUC) from baseline values. The parameters will be tested for normality by the Shapiro-Wilk test method. One-way ANOVA will be applied to describe differences between the groups. Student's paired t-test will be used to test for significant differences between subjects before and after sweetener intake. All statistical analysis will be done using the statistical software package, SPSS for Windows, Version 22.0 (SPSS Inc., Chicago, USA). Values will be reported as mean \pm SEM. Differences will be considered to be significant when P < 0.05. Statistics will be done by the principal investigator with support of Prof. [name], biostatistician.

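### LOCF for single missing blood values (Section 10.5) biases the affected participant's OGTT AUC and can enter a pre-treatment value as the post-treatment result

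*Protocol*

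**What the plan says.** Section 10.5 opens with a general rule, "as a basic principle, we will only analyse available data", and then adds one for laboratory data: "In case of single missing blood values, a 'last observation carried forward' (LOCF) approach will be used". It does not say which blood values are meant, or whether the carried value comes from the previous time point of the same curve or from the previous visit.

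The primary outcome consists of blood values. Section 4.1 sets the OGTT time points "for an accurate assessment of pharmacokinetics (AUC: area under the curve, Cmax, Tmax"). Section 8.2.1 adds to the fasting sample: "Further blood samples will be taken at regular time intervals (30, 60, 90, and 120 min"). Section 10.4.2 plans the analysis by "calculating the area under the concentration-time curve (AUC) from baseline values", followed by one-way ANOVA between groups and a paired t-test of before against after.

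In the schedule of assessments, lipids, ALAT/ASAT, hsCRP, IL-6, TNF-α, the TNF receptors, zonulin and LPS each have one measurement before treatment and one at V3.

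Two further statements limit the rule's reach. Section 10.4.1 says that "an analysis per protocol is planned", and Section 10.5 says of drop-outs: "Drop-outs will be replaced. Data from drop-outs will be included in the analysis if feasible".

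**The concern.** LOCF assumes that the quantity would have stayed where it was last seen. An OGTT is designed so that glucose, insulin and C-peptide move between samples, so the assumption fails by construction. A missing 30-min sample would be replaced by the fasting value, and a missing 90- or 120-min sample by an earlier and usually higher one. The same applies to 3-O-methyl-glucose. Its time-0 sample precedes ingestion, so carrying that value to 30 min records no absorption.

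For an analyte with one value per period, the only earlier observation is the pre-treatment one. Carrying it into V3 asserts that this participant did not change, and that assertion then enters the before-after comparison as data. This pilot is meant to inform larger studies, so biased changes would be passed on to their planning.

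**Working it through.** The protocol gives no figure for missing data, so there is nothing to reproduce. The check asks what the stated rule does to the stated endpoint.

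**Inputs.** Sampling times 0, 30, 60, 90 and 120 min (Sections 4.1 and 8.2.1); 20 participants per group (Section 10.2). Assumptions: the trapezoidal rule, and a glucose curve of 5.5, 9.0, 9.5, 8.0, 7.0 mmol/l. Section 10.4.2 does not make clear whether the AUC is total or baseline-subtracted, so both are shown.

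**Complete curve.** The trapezoidal weights are 15, 30, 30, 30, 15 min.
- Total AUC = 15×5.5 + 30×9.0 + 30×9.5 + 30×8.0 + 15×7.0 = 982.5.
- Baseline-subtracted AUC = 982.5 − 120×5.5 = 322.5.

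**One sample lost, LOCF within the curve.** The error is 30×(previous − true) at 30, 60 or 90 min, and 15×(previous − true) at 120 min. Linear interpolation between the neighbours is shown for comparison.

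| Lost sample | LOCF error | % total | % baseline-subtracted | Interpolation error | % total | % baseline-subtracted |
|---|---|---|---|---|---|---|
| 30 min | 30×(5.5−9.0) = −105 | −10.7 | −33 | 30×(7.5−9.0) = −45 | −4.6 | −14 |
| 60 min | 30×(9.0−9.5) = −15 | −1.5 | −4.7 | 30×(8.5−9.5) = −30 | −3.1 | −9.3 |
| 90 min | 30×(9.5−8.0) = +45 | +4.6 | +14 | 30×(8.25−8.0) = +7.5 | +0.8 | +2.3 |
| 120 min | 15×(8.0−7.0) = +15 | +1.5 | +4.7 | not applicable | | |

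**Sensitivity to the curve.** Three other assumed glucose curves (5.3/7.5/7.5/7.0/6.5, 5.5/9/9.5/8.5/7.5 and 5.5/10/9.5/7.5/6.0) give these LOCF errors in baseline-subtracted AUC:
- 30 min: −30% to −42%
- 60 min: −4% to +5%
- 90 min: +7% to +19%
- 120 min: +4% to +7%

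Interpolation on the same curves gives −13% to −23% at 30 min, −4% to −7% at 60 min and 0% to +2% at 90 min. Two assumed insulin curves (15/90/110/95/75 and 10/60/70/60/45) give LOCF errors of −27% to −28% at 30 min. At 60 min, LOCF and interpolation are about equal on both insulin curves.

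**V3 fasting sample lost.** No earlier point exists on that curve, so only a V2 value can be carried. In a baseline-subtracted AUC the time-0 value has weight 15 − 120 = −105 min. Each 0.1 mmol/l by which the V2 value exceeds the true V3 value therefore shifts the AUC by −10.5, which is 3.3% of 322.5.

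**Single-value analytes.** A carried pre-treatment value gives a change of exactly 0. If m of 20 are carried, and missingness is unrelated to the change, the mean change is multiplied by 1 − m/20: 0.95 for m = 1 and 0.80 for m = 4.

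**Group level, primary outcome.** Suppose one 30-min sample is lost among 20 participants with this curve. The arm's mean AUC moves by −105/20 = −5.25, which is −0.5% of 982.5 and −1.6% of 322.5.

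**The case against.** The strongest defence is that the rule is narrow and the damage small. It covers single missing values only. Drop-outs are replaced and the analysis is per protocol, so a wholly missed V3 is not filled. One lost tube in 20 moves an arm's mean AUC by about half a percent to under two percent, and Section 10.2 expects to detect only differences above 50%. All of this stands, and it limits the size of the point. It does not justify the rule: a participant who attends V3 and loses one tube is exactly the case that the rule addresses, and the result is wrong in a known direction.

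Some stronger readings are tempting but are not supported:

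- **That the two sentences of Section 10.5 contradict each other.** They read as a general principle followed by an exception. What is missing is the scope of the exception and the source of the carried value.
- **That Cmax and Tmax are distorted in the cases given here.** On the assumed curve the peak is 9.5 at 60 min, and losing the 30-, 90- or 120-min sample leaves both unchanged. They change only if the 60-min sample is lost, and interpolation then gives the same answer as LOCF (9.0 at 30 min).
- **That the change in the primary AUC is set to zero.** All five V3 samples would have to be carried from V2, which is not a single missing value.
- **That the SD of change is always understated.** With a fraction p set to zero at random, the variance is (1−p)s² + p(1−p)m², where m and s are the mean and SD of the true changes. This exceeds s² once |m|/s > 1/√(1−p), about 1.03 for p = 5%.
- **That glucose-tolerance results would be misclassified.** A carried 8.0 for a true 7.0 at 120 min does cross the 7.8 mmol/l limit in Section 4.1, but Section 10.4 plans no analysis of these categories.

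**Conclusion.** The point holds. Section 10.5 states an imputation rule that is unsuitable for the blood values to which it applies, and nothing in the protocol exempts the primary OGTT samples.

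For an affected participant, the AUC error is large at 30 min (−10.7% total and −33% baseline-subtracted on the main assumed curve) and moderate at 90 min (+4.6% and +14%). At 60 min it is small, and on that curve no worse than interpolation. The percentages rest on assumed curves. The direction does not: too low while the curve rises, too high while it falls.

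For single-value analytes, the inserted zero change follows from the design, because no other earlier value exists. For OGTT samples after time 0, carrying across visits is only one possible reading of an unspecified rule.

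The effect on group means depends on the number of lost samples, which the protocol does not give, and is small if few are lost. This is a rule worth correcting before the data are analysed. It is not a threat to the trial's conclusions as a whole.

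**What to change.** In Section 10.5, delete the LOCF sentence, keep the available-data principle, and add:

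- A single missing interior OGTT sample (30, 60 or 90 min) is filled by linear interpolation between its neighbours. This equals the trapezoidal AUC over the remaining samples, so it agrees with the available-data principle.
- If the 0- or 120-min sample is missing, the AUC for that visit is missing.
- No pre-treatment value is carried into V3. A missing V3 result for a single-value analyte stays missing.

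A repeated-measures model on the available OGTT samples may be added as a sensitivity analysis. Making it, or multiple imputation, the primary method would be more than this defect requires.

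The cost is one paragraph. A few participants will drop out of individual AUC or analyte comparisons. Interpolation is not exact either: at 30 min it still gives −14% in baseline-subtracted AUC on the main assumed curve, against −33% with LOCF.
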